Our two primary outcomes will focus on (1) overall health and (2) psychological distress. Our measure of overall health comes from an index based on responses to three survey questions: a self-reported rating of the participant's general health (on a 5 point Likert scale, ranging from poor to excellent); the self-reported number of days in the last 30 in which poor physical or mental health precluded engagement in the participant's usual activities; and a self-reported rating change in overall health outcomes over the last 12 months (three point scale denoting worse, same, or better). We will use the method of Anderson (2008) to create a single (standardized) index of overall health.⁷ This method uses the inverse covariance matrix of the variables to create the index and allows for missing observations.

Our measure of psychological distress is the Kessler-6 scale, a validated measure of non-specific psychological distress represented by the summed score of six questions querying the frequency of symptoms of feeling nervous, hopeless, depressed, restless, depressed, that everything was an effort, and worthless over the past 30 days.⁸ The Kessler-6 ranges from 0-24.

Secondary child health outcomes

In addition to the outcomes listed above, we plan to evaluate a series of secondary outcomes focused on child health and well-being, derived from a follow-up survey administered to participants with children ages 3 to 17 at the time of 24-month follow-up. These will include caregiver-reported child health, health care utilization, and several outcomes related to child well-being, neighborhood safety for children, and parenting, as listed in Table 2.

We will also examine additional child health outcomes for all children residing in IGNITE study clusters using secondary analysis of existing data sets. Specifically, we will assess school attendance and performance for all cluster residents using Philadelphia school district data, birth outcomes for cluster residents using Pennsylvania birth certificate data, and health care utilization outcomes for all cluster residents using electronic health record data from the Children's Hospital of Philadelphia. These outcomes are also included in Table 2. We will obtain separate approval from the Children's Hospital of Philadelphia Institutional Review Board prior to abstraction of electronic health record data for these child health outcomes.

Power Calculations

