For this cluster randomized trial, we assume a Type I error rate of 0.05 and a desired power of 0.8 for the primary outcomes. Our study will include 60 microclusters (30 intervention, 30 control) with at least 8 participants in each cluster (n=480 across all clusters). We will have no fewer than 480 and can enroll up to 720. The number of participants enrolled will depend on our dynamic enrollment strategy that we've discussed already. We assume an intraclass correlation (ICC) of 0.05. For our primary outcomes (and all survey-based outcomes), we will fit a marginal model using generalized estimating equations (GEE) to estimate the effect of the intervention relative to control. Under these assumptions, we will be able to detect an intervention effect of 0.33 s.d at 80% power with 30microclusters per arm (60 total) and 8 participants per microcluster.⁹ This is a conservative estimate of power since we will adjust for the baseline value of the outcome and other covariates associated with the outcome. If we are only able to sample from 50 microclusters (25 per arm; n=400 across all clusters), we will be able to detect a moderate effect size of 0.37 s.d. at 80% power. Assuming up to 25% attrition between baseline and endline, we would still be able to detect a treatment effect of 0.31 s.d.

Statistical Analysis

Individual-level primary and secondary outcomes

For all primary and secondary outcomes drawn from our two-wave survey of 720 trial participants, we will assess differences in outcomes between the intervention and comparison groups using Generalized Estimating Equation models (GEE) that account for clustering at the study microcluster level. We will use canonical link functions for all outcomes. All models will adjust for the baseline level of the outcome, all microcluster-level characteristics used in the covariate constrained randomization (see randomization protocol),¹⁰ any individual characteristics found to be imbalanced between the intervention and control groups at baseline.

We will conduct an intention-to-treat analysis: participants that move out of (or across) study clusters, separately engage with community partner services while in the control group, or do not engage with these services while in the treatment group will all be considered exposed to their original treatment assignment.

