Caregiver-Reported Child Health Composite Score	Child Health Questionnaire-28 (CHQ-28) Composite Score (Includes a series of questions focused on overall child health, activity limitation, emotional/behavioral difficulties, mood, relationships, and family cohesion)	Survey	Continuous (composite score)	24 months	
Caregiver-Reported Child Health	Rating of child health on a 5-point Likert scale, ranking from poor to excellent (CHQ-28)	Survey	Ordinal (poor, fair, good, very good, excellent)	24 months	
Health Care Utilization					
Well child care use	Caregiver report of number of well child visits in the preceding 12 months (National Survey of Children's Health)	Survey	Continuous (number of visits)	24 months	
Sick clinic visits	Caregiver report of number of sick clinic visits in the preceding 12 months (National Survey of Children's Health)	Survey	Continuous (number of visits)	24 months	
Emergency room visits	Caregiver report of number of emergency room visits in the preceding 12 months (National Survey of Children's Health)	Survey	Continuous (number of visits)	24 months	
Hospitalizations	Caregiver report of number of hospitalizations in the preceding 12 months (National Survey of Children's Health)	Survey	Continuous (number of visits)	24 months	
Usual source of care	Caregiver report of whether the child has a usual source of care (National Survey of Children's Health)	Survey	Binary (1 = yes)	24 months	
Forgone health care	Caregiver report of whether child needed but did not receive medical, mental health, dental, or vision care in the previous 12 months (National Survey of Children's Health)	Survey	Binary (1 = yes)	24 months	
Difficulty paying medical bills	Caregiver report of difficulty paying medical bills in the previous 12 months (National Survey of Children's Health)	Survey	Binary (1 = yes)	24 months	
Uninsurance or gaps in insurance in previous 12 months	Caregiver report of uninsurance or gaps in insurance in the previous 12 months (National Survey of Children's Health)	Survey	Binary (1 = yes)	24 months	

Child Well-Being				
Average sleep duration	Caregiver report of child's average sleep duration in the previous week (National Survey of Children's Health)	Survey	Categorical (Less than 7 hours, 7 hours, 8 hours, 9 hours, 10 hours, 11 hours, 12 or more hours)	24 months

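### Prespecify child age in every model for the 20 caregiver-reported child outcomes: they are measured only at 24 months, so the baseline-outcome term cannot be fitted, and no individual-level covariate replaces it

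*Combined protocol and SAP*

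**What the plan says.** Section 9, under Individual-level primary and secondary outcomes, describes GEE models clustered by microcluster for outcomes from the two-wave survey. The adjustment rule begins "All models will adjust for the baseline level of the outcome" and has two further parts: the microcluster characteristics used in the constrained randomization, and individual characteristics that turn out to be imbalanced at baseline.

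Two other statements extend the approach. The Power Calculations text applies GEE to all survey-based outcomes, and the multiplicity text applies similar methods to the survey-based secondary outcomes.

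The child measures are named as secondary outcomes, taken from "a follow-up survey administered to participants with children ages 3 to 17 at the time of 24-month follow-up". Table 2 lists the caregiver-reported items, for example "Caregiver report of number of well child visits in the preceding 12 months". Each has 24 months as its only timeframe. No child-specific model is written.

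The microcluster covariates (section 8.2, Randomization) are the area's age mix, gender, median income, unemployment, vacancy and tree canopy, all built from block-group data.

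**The concern.** A baseline value of the outcome is usually the strongest covariate in a model of this kind. The plan itself calls its power estimate conservative partly because of that adjustment. For the child survey outcomes there is no such value, and the plan names no substitute.

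The two remaining parts of the rule do little for an individual child. The share of an area's residents under 19 does not say whether the surveyed child is 4 or 16. The imbalance trigger refers to baseline, whereas the child survey is done only at follow-up, and no criterion for individual-level imbalance is stated. The 0.2 threshold in section 8.2 is for the microcluster covariates. Whether child age enters a model is therefore left to chance or to a decision taken after the data are seen.

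Age is an obvious candidate. The range 3-17 is an eligibility condition, and section 6 uses birthdays to choose up to three children per household. Sleep, screen time, outdoor play and well-child visits could plausibly depend on it. At stake are precision and prespecification across a set of 20 reported comparisons.

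**Working it through.** **1. Count the outcomes affected.** Caregiver-reported survey rows in Table 2: health 2, utilization 8, well-being 4, neighborhood safety 2, parenting 4. Total 2 + 8 + 4 + 2 + 4 = 20, all at 24 months only. By data type, 5 are labeled continuous (the CHQ-28 composite and four visit or hospitalization counts), 4 binary, 1 ordinal and 10 categorical. So 15 of the 20 are not continuous.

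**2. Reproduce the plan's own figure.** The documents give no power figure for child outcomes. The nearest is the survey figure: "we will be able to detect an intervention effect of 0.33 s.d at 80% power", with 30 clusters per arm, 8 participants per cluster and this assumption: "We assume an intraclass correlation (ICC) of 0.05".

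- Design effect = 1 + (8 - 1) x 0.05 = 1.35.
- SE of the difference in SD units = sqrt(2 x 1.35 / 240) = 0.1061.
- Two-sided alpha 0.05, normal quantiles: (1.960 + 0.842) x 0.1061 = 0.297. With t on 58 df: 0.302.
- Two-sided alpha 0.025: 0.327 (normal) or 0.334 (t).

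The stated 0.33 matches alpha 0.025, that is 0.05 split over two primary outcomes. The documents do not state that split. It does not match the stated 0.05. This does not affect the point here: the percentage change in the SE is the same at either alpha.

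**3. Effect of adjusting for child age.** Assumptions:

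- 480 children (the plan's target), 8 per cluster, ICC 0.05 borrowed from the adult outcomes.
- Age explains a share R2 of the within-cluster variance and none of the between-cluster variance.
- A linear model, with sibling correlation within households ignored.

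Variance = 2 x [(1 - ICC)(1 - R2)/(30 x 8) + ICC/30].

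With R2 = 0 the bracket is 0.95/240 + 0.05/30 = 0.003958 + 0.001667 = 0.005625. The within-cluster share is 0.003958/0.005625 = 0.704, so the SE ratio is sqrt(1 - 0.704 x R2).

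| Assumed R2 | SE ratio | SE reduction | Detectable effect (t, alpha 0.05) |
|---|---|---|---|
| 0 | 1.000 | 0 | 0.302 SD |
| 0.05 | 0.982 | 1.8% | 0.297 SD |
| 0.10 | 0.964 | 3.6% | 0.291 SD |
| 0.20 | 0.927 | 7.3% | 0.280 SD |
| 0.30 | 0.888 | 11.2% | 0.302 x 0.888 = 0.268 SD |

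**4. Sensitivity to the ICC.** The child ICC is not given. At R2 = 0.10 the detectable effect falls from 0.339 to 0.330 SD at ICC 0.10 (2.7%), and from 0.372 to 0.365 SD at ICC 0.15 (2.1%). A larger ICC shrinks the gain.

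**5. Upper case.** If age also removed between-cluster variance in the same proportion, the SE ratio would be sqrt(1 - R2), a reduction of 2.5, 5, 11 or 16% at R2 of 5, 10, 20 or 30%. Nothing in the documents supports that assumption.

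**The case against.** The strongest reply is about scope. The quoted sentence belongs to a paragraph on the two-wave survey, and the child survey is a separate single-wave instrument. A reader might infer that the plan contradicts itself by imposing an impossible term. The documents do not support that: the child outcomes are reached only through the broader statements on survey-based outcomes. The gap remains, however. Either the child models inherit a rule that cannot be followed, or they are GEE models with no stated covariates. Both readings call for the child model to be written down.

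A reader might also infer that the child models have no prognostic covariate at all. That goes too far. If the rule carries over, the area-level covariates and any imbalanced individual characteristics stay in. The power text also mentions other covariates associated with the outcome, though it names none.

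Three further objections stand:

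- The sqrt(1 - R2) figures overstate the gain when age acts within clusters. Neither they nor the table above carry over to the 15 outcomes that are not continuous.
- Chance age imbalance is not a second harm, because the unadjusted SE already includes it. With an assumed age SD of 4.3 years, the SE of the arm difference is 4.3 x 0.1061 = 0.46 years, or 0.11 SD of age. At R2 = 0.10 that moves an outcome by about 0.11 x sqrt(0.10) = 0.03 SD.
- A strong relation with age is not documented for any item. It is least obvious for household or neighborhood items such as medical bills or neighbors watching out for children.

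Data availability also limits the remedy. Child sex is not listed as collected. The documents do not clearly say that the up to 240 additional caregivers complete the adult baseline survey.

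**Conclusion.** The point holds as a free improvement. For all 20 caregiver-reported child outcomes the baseline-outcome term cannot be fitted, no replacement is given, and no child-level or other individual-level prognostic covariate is prespecified. Fixing child age in advance is better than letting it enter only when it looks imbalanced.

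The size is modest: about 2 to 11% off the SE of a continuous outcome for R2 between 5 and 30%. This rests on an assumed R2, an ICC borrowed from the adult outcomes and 8 children per cluster. The proportional gain for binary, ordinal and categorical outcomes is not quantified here.

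A reader might infer that the unadjusted child comparisons are biased. They are not made so by this gap, since assignment remains randomized. These are secondary outcomes, and the plan claims power only for the primary ones: "we assume a Type I error rate of 0.05 and a desired power of 0.8 for the primary outcomes".

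**What to change.** Add a short paragraph to section 9 for the child survey outcomes:

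- Drop the baseline-outcome term for the 20 caregiver-reported outcomes in Table 2.
- Include child age at the 24-month survey in a fixed form, such as bands 3-5, 6-11 and 12-17, in every child model regardless of observed balance. Check that the bands cover every surveyed child, since section 6 applies the 3-17 range at recruitment.
- Keep the microcluster covariates.
- Add child sex only if it is recorded.
- Add the caregiver's baseline health index and Kessler-6 only if they are available for all child-survey caregivers, or if a rule for missing values is stated.

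Confirm that the child's age or birth date is stored as a variable. The selection rules imply that it is known but do not say that it is recorded.

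The cost is SAP wording before analysis and a few degrees of freedom. For logit models the adjusted estimate is a conditional odds ratio, and the report should say so.

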Neighborhood microclusters (hereafter, microcluster) served as the intervention unit for the study. To form these microclusters, a master list of every block, or street segment from one intersection to the next intersection, in the 75 eligible census tracts was created. A total of 8,462 blocks were included in the master list. A shapefile of selected blocks was imported into R. A random block was chosen as an index block and a 0.125 (one eighth) mile diameter buffer was created around that block. All other blocks that fell within this radius were used to form a microcluster of geographically proximal blocks. A block was included in the microcluster if at least half of the street segment fell within the microcluster boundaries. This microcluster formed a study area. All blocks that were included in the microcluster were removed from the master list to ensure no overlap of microclusters. Next, an additional 0.125-mile exclusion zone buffer was created on all sides of each microcluster. The purpose of the exclusion zone was to create an additional buffer between microclusters to minimize potential spillover effects from the interventions. This process was then repeated until 60 total non-overlapping microclusters were in each city section.

Our goal was to have a final set of microclusters that minimized overlap of microcluster exclusion zones to reduce potential spillover and contamination effects across trial arms. To do this in a random manner, the process to create 60 study microclusters with 0.125-miles exclusionary zones was repeated 1,000 times to create 1,000 unique maps. An analysis was run to determine the total area of exclusion zone buffer overlap for each of the 1,000 microcluster map iterations, which was then ordered from lowest to highest. We then selected the bottom microcluster iterations with the lowest exclusion zone overlap. From this list, one iteration was selected at random to determine final study sites.

Randomization

We randomly assigned the 60 microclusters to treatment (intervention, n=30 microclusters) and control (nonintervention, n=30 microclusters) groups. Prior to randomization, microclusters were stratified by city section (West and North). The land area and number of streets in each section was near-equal, allowing for stratification pre-constrained randomization.¹

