Within the city section strata, we conducted a covariate-constrained randomization process in order to ensure balance between microclusters randomized to intervention and those randomized to control based on relevant sociodemographic variables. Covariate-constrained randomization quantifies baseline imbalance of microcluster-level covariates (both categorical and continuous) across all microclusters using a balance metric and then randomly selects one randomization schema from those with acceptable balance. Furthermore, the intraclass correlation coefficient calculation – a measure of reliability – remains unaffected under a constrained randomization model.²

We chose the following covariates to balance on: age (categorized by shares under age 19, 19-49, 50-64, and 65 and above); gender; median income; unemployment rate; amount of vacancy; and tree canopy. We did not balance on race/ethnicity (e.g., % Black) or poverty rates, since initial criteria for study site selection focused on census tracts whose populations were at least 80% Black and with elevated poverty rates. The covariates were measured based on their distribution of means by each microcluster using block group data from the US Census Bureau's 2020 ACS. Each microcluster's mean is the weighted mean for the covariates based on percent of land area in each census block group in which the microcluster sits. A microcluster could be in one census block group or could cross over 2 or 3 census block groups. Following the literature, we used a threshold of 0.2 for standardized mean differences in the covariates.

We used the -cvcrand- package, specifically the -cvrall- function, in R to calculate the final covariate balance metric and selection schema at random after covariate balance by cluster was achieved.²

Enrollment

Participant recruitment will commence in September 2023 and will run through May 2023 (or until we enroll at least 480, but no more than 720, in the main trial). Recruitment in control and intervention microclusters will occur simultaneously. The data analyst who performed the randomization will randomize microcluster order (stratified by intervention and control status and city section) to determine the order in which recruitment occurs.

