Given that our study includes two primary outcomes, we will address for simultaneous inference using a stacked GEE approach.¹¹ This approach adequately covers family-wise Type I errors in a manner that is more efficient than overly conservative approaches such as Bonferroni-Holm.

We will use a similar set of approaches for the survey-based secondary outcomes. For these outcomes we will report both unadjusted p-values as well as p-values adjusted for multiple inference (again based on models using a stacked GEE approach).

Will conduct four sensitivity analyses. First, we will assess for non-random attrition by regressing a binary indicator for each participant equal to 1 if the participant did not complete a follow-up survey on the treatment indicator, microcluster level attributes used in the covariate constrained randomization procedure, and any individual-level covariates that were not balanced at baseline (adjusting standard errors for clustering at the microcluster level). In the event of non-random attrition (denoted by a statistically significant coefficient on the treatment indicator from the above regression), we will use inverse probability weighing approaches (IPW) to address potential biases. We will also use an alternate strategy that calculates the lower bound of treatment effects by assigning the "best" (i.e., most positive) sample value of an outcome to attritors in the control group and "worst" sample value of an outcome to attritors in the treatment group.¹²

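### Family-wise error control is asserted for GEEs with about eight cluster-level covariates on 60 clusters, but no small-sample variance, working correlation or reference distribution is named

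*Combined protocol and SAP*

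**What the plan says.** Under Individual-level primary and secondary outcomes (section 9), survey outcomes are analysed by GEE clustered on microcluster. The covariate rule is "All models will adjust for the baseline level of the outcome, all microcluster-level characteristics used in the covariate constrained randomization", plus "any individual characteristics found to be imbalanced between the intervention and control groups at baseline".

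The balancing covariates are listed in section 8.2, Randomization: "We chose the following covariates to balance on: age (categorized by shares under age 19, 19-49, 50-64, and 65 and above", followed by gender, median income, unemployment, vacancy and tree canopy. City section was handled separately: "Prior to randomization, microclusters were stratified by city section (West and North". It is not on the balance list, although the constraint operated inside the strata: "Within the city section strata, we conducted a covariate-constrained randomization process".

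The two primary outcomes are tested jointly with a stacked GEE, preferred to Bonferroni-Holm for efficiency, and the plan says "This approach adequately covers family-wise Type I errors". Survey-based secondary outcomes follow a similar approach. The Power Calculations set Type I error at 0.05 and allow for a smaller trial: "If we are only able to sample from 50 microclusters (25 per arm; n=400 across all clusters".

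No section states a working correlation, variance estimator, small-sample correction, reference distribution or degrees of freedom for these models. The third sensitivity analysis is a permutation analysis that drops all covariates and reshuffles treatment 1:1 across microclusters.

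**The concern.** A GEE sandwich variance is justified as the number of clusters grows. Sixty clusters would usually be adequate for a model with little in it, but this model spends many cluster-level parameters. They shrink the cluster residuals from which the sandwich is built, so the standard error of the treatment effect comes out too small unless it is corrected.

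Because the plan is silent, two analysts could both follow it faithfully, one testing the primary outcomes at a true family-wise error near 5% and the other near 9%. The same models serve the survey-based secondary outcomes, so the ambiguity carries over to those adjusted p-values.

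**Working it through.** **1. The plan's own figure.** Detectable effect = (critical value for alpha + critical value for power) × sqrt(2[1+(m−1)ICC]/(km)). With k = 30 per arm, m = 8 and ICC 0.05, the root is sqrt(2 × 1.35/240) = 0.106. The effect is 2.80 × 0.106 = 0.297 SD (normal) or 0.302 SD (t, 58 df), not the stated 0.33. The stated 0.33 and 0.37 are matched at alpha 0.025 with t (0.334, and 0.368 at 25 per arm), or roughly with 6 per cluster at alpha 0.05 (0.330 and 0.362, normal). The plan should say which was used, but nothing below depends on it. The calculation allows for clustering, not for the number of cluster-level terms or how variance is estimated, so it does not support the coverage statement.

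**2. Parameter count.** Four age shares sum to one, leaving 3 free; with gender, income, unemployment, vacancy and canopy that is 8. Adding intercept, treatment and section gives p = 11. Residual df: 60 − 11 = 49, or 50 − 11 = 39.

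**3. Hand approximation.** On average the uncorrected sandwich understates the variance by a factor (K − p)/K, so the effective critical value is the nominal one times sqrt((K − p)/K). Tail areas are read from t on K − p df. Family-wise values use an outcome correlation of 0.6 (assumed), with critical values 2.199 (normal), 2.263 (t, 49 df) and 2.280 (t, 39 df).

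- K = 60, p = 11: factor sqrt(49/60) = 0.904. Normal: 1.960 × 0.904 = 1.771, giving 8.3% per outcome; 2.199 × 0.904 = 1.987, giving 9.1% family-wise. t only: 2.263 × 0.904 = 2.045, giving 8.1% family-wise.
- K = 50, p = 11: factor 0.883, giving 9.1% per outcome and 10.2% family-wise (normal); 8.8% family-wise (t only).
- K = 60, p = 2 (no cluster covariates): factor 0.983, giving 5.9% and 6.1% (normal).

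**4. Simulation.** Taken from the plan: 60 or 50 clusters, ICC 0.05, two strata, standardized differences below 0.2. Assumed: 30 clusters per section, baseline-endline correlation 0.5, outcome correlation 0.6, exchangeable working correlation, section in the model. There were 4,800-6,000 null trials per setting (Monte Carlo SE about 0.4 points at 9%, 0.3 at 5%). The skewed rows treat the Kessler-6 as a bounded count ("The Kessler-6 ranges from 0-24") and drive half the second outcome by a zero-heavy day count.

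| Family-wise error, % | Uncorrected, normal | Uncorrected, t | Kauermann-Carroll, t | Adjusted permutation |
|---|---|---|---|---|
| 60 × 8 | 8.9 | 8.1 | 4.8 | 4.6 |
| 60 × 8, repeat run | 9.3 | 8.4 | 5.7 | 5.4 |
| 60 × 8, 25% attrition | 9.8 | 8.6 | 5.1 | 4.8 |
| 60 × 8-12, skewed | 8.9 | 7.9 | 4.8 | 4.9 |
| 60 × 8-12, skewed, 25% attrition | 10.0 | 8.7 | 5.3 | 5.2 |
| 60 × 8, no balance constraint | 10.1 | 9.1 | 5.6 | 5.3 |
| 50 × 8 | 10.1 | 8.5 | 4.8 | 4.5 |
| 60 × 8, no cluster covariates | 6.5 | 5.6 | 4.9 | not run |

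A separate simulation used outcome correlation 0.5, a different allocation rule and 5,000 trials per setting. With the uncorrected sandwich and normal reference it gave 8.0% per outcome and 8.8% family-wise without section; 8.8% and 10.4% with section; 11.0% family-wise at 50 clusters; and 6.4% without cluster covariates. Mancl-DeRouen with t was conservative throughout (2.3-3.1% family-wise).

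**5. Source of the excess.** Removing the cluster terms takes 8.9% to 6.5%, which is 2.4 of the 3.9 excess points. Going from one outcome to the stacked test adds only about 1 point (8.0 to 8.8; 8.8 to 10.4).

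**6. The permutation analysis.** It is a sensitivity analysis, fits no covariates, and does not mention strata or the constrained set. It therefore gives no reference distribution for the adjusted primary test. The plan also compares point estimates across the two analyses and reads differences as confounding; that does not check the primary p-value.

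**The case against.** The strongest reply is that nothing in the plan says the uncorrected sandwich or a normal reference will be used. It cites methods papers for the constrained-randomization adjustment and for the stacked GEE, and either may prescribe a correction; they cannot be seen here. That stands. A reader might infer that the trial's family-wise error is about 9%, but the documents do not support that. They support only that the method is unspecified and the assurance unbacked.

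Second, the coverage sentence concerns multiplicity. A reader might infer that stacking fails to control family-wise error. The figures do not show that: the inflation is already about 8% for a single outcome, so the root is the adjusted model, not the stacking.

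Third, the permutation analysis is a partial safeguard, because a primary result it does not support would be visible. That is fair, but it leaves the primary test as it is.

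Fourth, since the constraint was applied within city section, an analyst might include section anyway. Also fair: that part is a clarification.

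Two further inferences should be resisted.

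- *That choosing individual covariates by observed imbalance is an error to be replaced by a fixed list.* It is a trade-off. Under assumed prognostic strength (five candidates, joint R² 5-15%), a fixed list gains 1.1-3.3 power points. If recruitment truly shifted one such variable by 0.2 SD, bias is 0.004-0.007 SD under the plan's rule but 0.019-0.034 SD under a fixed list that omits it.
- *That recruitment overlapped visible place-based work.* The dates conflict. Section 6 runs recruitment from September 2022 to March 2024. Section 8.2, Enrollment gives September 2023 through May 2023. Follow-up at 24 months between September 2024 and March 2025 implies enrolment ended by March 2023, before the April 2023 start of place-based work.

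**Conclusion.** The concern holds as a gap in specification. The plan asserts family-wise coverage for a model with about eight cluster-level covariates on 60 clusters without naming the choices that decide whether the assurance is true. If the uncorrected sandwich with a normal reference is used, error is about 8-9% per outcome and 8-10% family-wise at 60 clusters, and about 10-11% family-wise at 50. With a t reference alone it is about 7-9% at 60 clusters. A Kauermann-Carroll correction with t brings it to about 5-6%.

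These figures rest on the plan's ICC of 0.05 and on assumed outcome and baseline correlations. Two simulations with different settings and the hand approximation agree closely. Omission of city section from the listed covariates is a minor addition, not a second source of error.

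**What to change.** (a) For the single and stacked survey GEEs, pre-specify an exchangeable working correlation and a bias-corrected sandwich, for example Kauermann-Carroll. Use a t (single) or multivariate-t (stacked) reference on clusters minus cluster-level parameters: 49 df at 60 clusters with section included, 39 at 50. A covariate-adjusted permutation test of the maximum statistic, restricted to the stratified, constrained allocation space, would serve equally well. Name the correction, since Mancl-DeRouen with t is noticeably conservative here.

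(b) Together with (a), include a West/North indicator in every survey-outcome GEE. Without (a) this raises the uncorrected error (8.8% to 10.4% in the simulation above). The power gain at 0.33 SD is 0-0.2 points if a section difference of 0.1-0.2 SD is already in the baseline outcome, and larger if it is not.

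Optionally, state the candidate individual covariates and the imbalance threshold; the rule itself can stay.

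Cost: wording and standard software options. By the approximation above, intervals are about 13% wider than uncorrected normal ones: 2.010/(1.960 × 0.904) = 1.13. The df change alone moves the detectable effect only from 0.302 to 0.303 SD. Under the simulation assumptions, corrected per-outcome power at 0.33 SD and the family-wise critical value is 89.5%, or 81.2% with 25% attrition. Hand check at an SE of 0.095: 0.33/0.095 − 2.263 = 1.21, or 88.7%. Power for both outcomes together is 83% and 72%.
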